7. ELIGIBILITY CRITERIA

- *Describe the characteristics of the subject population, including their anticipated number, age, ranges, sex, ethnic background, and health status. Identify the criteria for inclusion or exclusion of any subpopulation.*
- *Explain the rationale for the involvement of special classes of subjects, such as fetuses, pregnant women, children, prisoners or other institutionalized individuals, or others who are likely to be vulnerable. You cannot include these populations in your research, unless you indicate such in the protocol*
- *Similarly, detail exclusionary criteria: age limits, special populations (minors, pregnant women, decisionally impaired), use of concomitant medications, subjects with other diseases, severity of illness, etc.*

- We anticipate recruiting 80 subjects for this study. We anticipate a fair distribution of males and females, Caucasians, African Americans, and people from other ethnic groups. We anticipate that most patients in this age group are relatively healthy with possibly 1-5 past medical health problems.
- Inclusion Criteria: patients who are 18 years and older with the ability to speak and understand English and with T2DM AND CKD stages 3b-5. Vulnerable populations would include elderly and minorities, as listed in section 26 below for vulnerable populations. There are minimal risks of participating in this study for all subjects including vulnerable populations.
- Exclusion criteria: patients with Type I DM, ESRD on HD, hemoglobinopathies, who have received red blood cell transfusions in the last 12 weeks, with hemoglobin <9, current use of acetaminophen on a daily basis, steroid treatment in the prior 12 weeks, greater than 50% change in diabetes medications or new diabetes medications started in the prior 12 weeks, patients who are currently pregnant.

8. NUMBER OF SUBJECTS

- *Indicate the total number of subjects to be accrued locally. If applicable, distinguish between the number of subjects who are expected to be pre-screened, enrolled (consent obtained), randomized and complete the research procedures.*
- *If your study includes different cohorts, include the total number of subjects in each cohort.*
- *If this is multisite study, include total number of subjects across all sites.*

There is an expected number of 80 recruited subjects from all aforementioned sites (Northwell Health Division of Nephrology, Division of Endocrinology, and Winthrop University Hospital Division of Nephrology).
We expect all patients will complete the research procedures

9. STUDY TIMELINES

- *Describe the duration of an individual's participation in the study*
- *Describe the duration anticipated to enroll all study subjects*
- *The estimated date of study completion*

- An individual patient's participation in this study will be for 14 days
- We anticipate enrolling study subjects from September 2017 to May 2018.
- The estimated date of study completion will be June 30, 2018

10. ENDPOINTS

- *Describe the primary and secondary study endpoints*
- *Describe any primary or secondary safety endpoints*

- Primary End-Points: 1) Correlation between HbA1c and mean glucose concentration measured by CGM; 2) Characterization of hypoglycemic events, number, severity and duration. (Also, a safety end-point).
- Secondary End-Points: 1) Correlation between serum fructosamine and mean glucose concentration measured by CGM, 2) Determination of HbA1c and serum fructosamine regression equation, slope, Y intercept, average glucose at different test levels, 3) Number of hyperglycemic events and duration of each hyperglycemic event, 4) Study glucose variability as measured by mean amplitude of glucose excursion

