Diabetes control is often assessed by tests of glucose levels over time, such as the glycosylated hemoglobin A1c (HbA1c) and fructosamine. In the later stages of chronic kidney disease (CKD) there is limited data available on the utility of these tests. There are reasons to believe that the tests may be less accurate in this population. Continuous glucose monitoring (CGM) offers an effective method for understanding the totality of glucose exposure and incidence of both hyperglycemic and hypoglycemic excursions. In the proposed study we plan to utilize CGM in patients with late stage CKD stages 3b-5 to 1) determine accuracy of HbA1c and serum fructosamine testing as measures of glucose control in patients with Type 2 Diabetes Mellitus (T2DM), 2) better understand test characteristics in the late stage CKD population (correlation, linear equation, slope, Y intercept, average glucose at different HbA1c levels), 3) develop a preliminary understanding of how test characteristics differ in late stage CKD compared to other patients with diabetes, 4) quantify time burden and number of episodes of hypoglycemia, 4) study hyperglycemic burden and 5) analyze glucose variability. The research staff will explain the study to patients that meet all inclusion criteria. Patients will get time to understand the study, review the consent document, ask questions to the PI, and then provide their consent to participate in the study. On Day 1 of the study, a CGM (Freestyle Libre) device will be placed on patients with CKD 3b-5 which will be worn for 14 consecutive days. Patients will return on Day 14 to remove the CGM device. HbA1c and fructosamine values will be drawn on Day 14 and these results will be compared with average glucose monitoring values as recorded on the CGM device. Incidence, duration, and severity of both hypoglycemic and hyperglycemic events will be analyzed. It is our hypothesis that there will be significant variability in the serum HbA1c values when compared with calculated HbA1c from CGM readings. We also hypothesize that the results will reflect a greater incidence of hypoglycemia in this population by CGM analysis.

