4. OBJECTIVE(S)/SPECIFIC AIMS AND HYPOTHESES

- *A concise statement of the goal(s) of the current study.*
- *The rationale for and specific objectives of the study.*
- *The goals and the hypothesis to be tested should be stated.*

- The goals of our study is to 1) determine accuracy of HbA1c and serum fructosamine testing as measures of glucose control, 2) better understand test characteristics in the late stage CKD population (correlation, linear equation, slope, Y intercept, average glucose at different HbA1c levels), 3) develop a preliminary understanding of how

test characteristics differ in late stage CKD compared to other patients with diabetes, 4) quantify time burden and number of episodes of hypoglycemia, 5) study hyperglycemic burden and 6) analyze glucose variability.

- It is our hypothesis that there will be significant variability in the serum HbA1c values when compared with calculated HbA1c from CGM readings. It is our hypothesis than the incidence of hypoglycemia will be high in patients with CKD 3b-5.

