12. STATISTICAL ANALYSIS

- *Describe how your data will be used to test the hypotheses.*
- *State clearly what variables will be tested and what statistical tests will be used.*
- *Include sample size calculations.*
- *If this is a pilot study, state which variables will be examined for hypothesis generation in later studies.*

Patients with less than 7 days of CGM measurements will be excluded from analysis. Arithmetic mean glucose (AMG) will be calculated for each patient from

all CGM glucose measurements. A simple linear regression model will be applied to estimate the relationship between AMG and HbA1c. Once the relationship is established through the model, prediction of mean AMG together with 95% confidence intervals will be calculated at different levels of HbA1c. Influence of factors such as age, gender on the relationship between HbA1c and AMG will be examined through a multivariate regression model. Slopes and intercepts of the regression equations for the individual subgroups will be compared to those of the simple linear regression model. A quadratic regression model will also be applied if the relationship between the two variables is not linear. The same analysis will be performed to establish the relationship between AMG and serum fructosamine. Linear and quadratic regression models will be applied to estimate the relationship between AMG and HbA1c and serum fructosamine. If a linear relationship is established then slope, Y-intercept and correlation coefficient will be calculated. Mean AMG at different levels of HbA1c and serum fructosamine will be calculated. Glucose variability will be calculated as MAGE scores. First all the local maximum/minimum values are determined. The next step is an assessment of maximum/minimum pairs against the standard deviation (SD). If the difference from minimum to maximum is greater than the SD, this variation from mean measure is retained. If the local maximum/minimum is less than 1 SD it is excluded from further calculations. These troughs are retained and summed to achieve the MAGE score.

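### Primary end-point 1 is a correlation whose value moves with the spread of HbA1c and glucose among enrolled patients, and it is the only planned summary of individual scatter

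*Combined protocol and SAP*

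**What the plan says.** Section 10 names the "Correlation between HbA1c and mean glucose concentration measured by CGM" as primary end-point 1. The regression equation, slope, intercept and average glucose at given test levels are secondary.

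Section 2 sets the aim to "better understand test characteristics in the late stage CKD population (correlation, linear equation, slope, Y intercept, average glucose at different HbA1c levels", with correlation first in the list. Section 4 repeats this and adds, as a preliminary aim, to learn how "test characteristics differ in late stage CKD compared to other patients with diabetes". Its first goal is to "determine accuracy of HbA1c and serum fructosamine testing as measures of glucose control". Its hypothesis is that "there will be significant variability in the serum HbA1c values when compared with calculated HbA1c from CGM readings".

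Section 7 admits "patients who are 18 years and older with the ability to speak and understand English and with T2DM AND CKD stages 3b-5". Neither the inclusion nor the exclusion criteria contain an HbA1c limit, stratum or quota. Sections 5 and 6 draw patients from nephrology and endocrinology practices without fixing the mix.

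Section 12 fits a simple linear regression of arithmetic mean glucose (AMG) and HbA1c, with a quadratic model if the relation is not linear. It gives 95% confidence intervals for mean AMG at several HbA1c levels, and then: "If a linear relationship is established then slope, Y-intercept and correlation coefficient will be calculated". Fructosamine is handled the same way. Section 12 mentions no residual SD, no prediction interval for an individual patient, and no marker or AMG SD to accompany r. No section says how a given value of r will be interpreted.

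**The concern.** A correlation mixes two things: how tightly glucose follows the marker, and how widely the sampled patients differ. If the enrolled patients happen to have similar HbA1c values, r falls. If a few very high values are enrolled, r rises. Neither change says anything about HbA1c in kidney disease.

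This matters here because the plan calls r a characteristic of the test in CKD and intends some contrast with other patients with diabetes. No comparator cohort is described, so any such contrast would use values from elsewhere, where the spread need not match. A difference in case mix could then be read as an effect of CKD.

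The first goal and the hypothesis concern how far individual HbA1c values depart from what CGM shows. The planned line and its confidence intervals do not display that.

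**Working it through.** **Plan's own figure.** There is none to reproduce. The documents give no expected r, no HbA1c SD, no slope, no residual SD and no sample-size calculation. Only the planned 80 subjects (section 8) comes from the documents. Every other input below is an assumption, as is the unit mg/dL.

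**Step 1: r against HbA1c spread, test performance held fixed.** Let AMG = a + b·HbA1c + error, with residual SD s. Then

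r = b·SDx / √((b·SDx)² + s²), where SDx is the SD of HbA1c in the sample.

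For b = 25 mg/dL per 1% and s = 25 mg/dL this reduces to SDx / √(SDx² + 1):

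| HbA1c SD (%) | 0.8 | 1.0 | 1.2 | 1.5 | 2.0 |
|---|---|---|---|---|---|
| r | 0.62 | 0.71 | 0.77 | 0.83 | 0.89 |

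Over the same SDs, r runs from 0.54 to 0.85 at b = 20, and from 0.69 to 0.92 at b = 30.

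**Step 2: compare with sampling error.** The Fisher z interval has half-width 1.96/√77 = 0.223 on the z scale. With all 80 patients analysed, r = 0.70 has a 95% CI of 0.57 to 0.80, a width of 0.23. The shift in r is 0.83 − 0.71 = 0.12 for HbA1c SDs of 1.0 to 1.5%, about half that width. For SDs of 0.8 to 2.0% it is 0.89 − 0.62 = 0.27, slightly more than that width. At these two extremes the intervals (0.46 to 0.74 and 0.83 to 0.93) do not overlap.

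**Step 3: what the planned intervals show.** With s = 25, n = 80 and t = 1.99 on 78 df, at the mean HbA1c:

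- CI for mean AMG: ±1.99 × 25/√80 = ±5.6 mg/dL.
- Interval for one patient: ±1.99 × 25 × √(1 + 1/80) = ±50 mg/dL.

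The first narrows as n grows; the second does not shrink below the scatter. Only the first is planned.

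**Step 4: precision of the residual SD.** The 95% chi-square multipliers on 78 df are 0.865 and 1.186. An estimate of 25 mg/dL would have an interval of about 21.6 to 29.7 mg/dL.

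**Step 5: is the residual SD free of spread?** Only under Step 1's model, where case mix varies through HbA1c and scatter is constant. Suppose instead that case mix varies through glucose and HbA1c carries the error: HbA1c = a + AMG/30 + e, with SD(e) = 1.0%. Then var(HbA1c) = (SD(AMG)/30)² + 1, and the residual SD is SD(AMG)·√(1 − r²):

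| SD(AMG), mg/dL | var(HbA1c) | r | Slope of AMG on HbA1c | Residual SD, mg/dL |
|---|---|---|---|---|
| 15 | 1.25 | 0.45 | 6 | 13.4 |
| 30 | 2.00 | 0.71 | 15 | 21.2 |
| 60 | 5.00 | 0.89 | 24 | 26.8 |

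Here r, slope and residual SD all move although the test is unchanged.

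Rescaling r to a common HbA1c SD also fails in this setting. Take SD(e) = 0.8% and move from SD(AMG) 60 to 20. The true r at 20 is 0.667/√(0.444 + 0.64) = 0.64. The usual formula r·k/√(1 − r² + r²k²), with r = 0.93 (0.9285 unrounded) and k = 1.041/2.154 = 0.483, returns 0.77.

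**Step 6: constant bias.** Subtracting 1.0 point from every HbA1c value leaves r unchanged (0.712 before and after in a simulated sample). It shifts only the intercept, so the residual SD is unchanged too.

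**The case against.** The strongest reply is that the plan already contains more than r. Slope, intercept and mean AMG by HbA1c level are planned, and under Step 1's model the HbA1c spread does not distort them. That stands. A reader might infer that section 12 offers nothing free of the spread, and the text does not support that. What is missing is narrower: a measure of individual scatter other than r.

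A reader might also infer that end-point 1 fails the study's goals, or that the plan will test r against an outside r. Neither follows. Goal 2 names correlation as something to describe, so reporting r delivers that part. The cross-population aim is only to "develop a preliminary understanding of how test characteristics differ in late stage CKD compared to other patients with diabetes", and section 12 specifies no comparison of r with another population. The risk lies in how r may be read, not in a planned analysis.

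For the comparison the study can make itself, HbA1c against fructosamine in the same patients, r is adequate for ranking. Under straight-line fits the residual SD equals SD(AMG)·√(1 − r²), apart from a degrees-of-freedom factor common to both markers, so both measures give the same order.

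Finally, it is tempting to present the residual SD as immune to case mix. Step 5 shows that this depends on how case mix varies, which the documents do not settle: study HbA1c is drawn on Day 14 and is not an entry criterion.

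**Conclusion.** The concern holds in a limited form. End-point 1 is a raw correlation described as a test characteristic, its value depends on an uncontrolled spread of HbA1c and glucose, and nothing else planned summarises individual scatter.

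The dependence is algebraic; its size rests on assumptions. With slope and residual SD both at 25, a moderate difference in HbA1c spread (1.0 against 1.5%) moves r by 0.12. It takes the wide span of 0.8 to 2.0% to exceed the width of the sampling interval. These figures also assume a straight line, equal scatter and 80 analysed patients.

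The remedy improves reporting and does not rescue a failed design. The residual SD and prediction interval show scatter in glucose units, but they are not guaranteed to carry over between populations. Like r, the residual SD cannot reveal a constant HbA1c bias, so neither alone settles the accuracy goal.

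**What to change.** In sections 10 and 12:

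- Report with end-point 1 the residual SD of AMG around the HbA1c line (mg/dL, with 95% CI) and the 95% individual prediction interval for AMG at stated HbA1c levels. Name these as the main measures of how closely HbA1c tracks glucose.
- Do the same for fructosamine, so that both markers are on the AMG scale.
- Keep r as descriptive, always printed with the SD and range of the marker and of AMG.
- State that a difference in r from another population will not by itself be attributed to CKD. Do not prescribe rescaling of r as the condition for such a comparison, and do not describe the residual SD as independent of the spread.
- State that the residual SD, like r, does not detect a constant HbA1c bias.

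Cost: a few sentences and a little more reporting. The figures come from the regression already planned, with no new data, visits or patients. The downside is a headline figure in mg/dL that is less familiar than r.

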- The FreeStyle Libre Pro Flash Glucose Monitoring System is a professional continuous glucose monitoring (CGM) device indicated for detecting trends and tracking patterns in persons (age 18 and older) with diabetes. The Freestyle Libre Pro device is FDA approved (PMA# P150021). Participants will use the FreeStyle Libre Pro Flash Glucose Monitoring device according to its approved use, on the back of the arm.
- CGM monitoring will be performed on Day 1 by placing the Freestyle Libre Pro on research subjects for intended use of 14 days.
- Subjects will be advised to return to the research site on Day 14 to remove the CGM device for analysis. On Day 14, blood will be drawn for HbA1c and fructosamine, funded by internal research funds and there will be no charge to the patient. The blood drawn for this research will be approximately 10-15 milliliters.
- There are no drug washout periods. Subjects will continue to take all their medications and/or insulins as prescribed by their doctor.
- Baseline data including age, race, ethnicity, past medical history, home medication list, and diabetes related laboratory data will be collected from Allscripts medical records. No personal identifying information will be collected.

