16. WITHDRAWAL OF SUBJECTS

- *Describe anticipated circumstances under which subjects will be withdrawn from the research without their consent*
- *Describe procedures for orderly termination*
- *Describe procedures that will be followed when subjects withdraw from the research, including partial withdrawal from procedures with continued data collection.*

During the monitoring phase, the diabetes medications will not be changed unless indicated by their private endocrinologist or internist, in which case the patient will be withdrawn from the study for fulfilling an exclusion criterion. Furthermore, patients with less than 7 days of CGM measurements will be excluded from statistical analysis due to limited data collection.
--

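### The hypo- and hyperglycemia endpoints are numbers of events with no time denominator, although analysed patients may have anywhere from 7 to 14 days of sensor data

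*Combined protocol and SAP*

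**What the plan says.** All references are to the combined protocol and SAP.

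- **Endpoints (Section 10).** The second primary endpoint, also labelled a safety endpoint, is "Characterization of hypoglycemic events, number, severity and duration". The third secondary endpoint is "Number of hyperglycemic events and duration of each hyperglycemic event". Neither has a unit of time.
- **Objectives (Section 4).** One aim is to "quantify time burden and number of episodes of hypoglycemia". The hypotheses in Sections 2 and 4 speak of the incidence of hypoglycemia, but incidence is nowhere defined as a rate.
- **Planned wear (Section 11).** The sensor is fitted on Day 1, "placing the Freestyle Libre Pro on research subjects for intended use of 14 days".
- **Who is analysed (Section 12).** "Patients with less than 7 days of CGM measurements will be excluded from analysis". Section 16 repeats the rule: "patients with less than 7 days of CGM measurements will be excluded from statistical analysis due to limited data collection".
- **Analysis (Section 12).** It covers regressions of mean glucose on HbA1c and on fructosamine, and the MAGE calculation. It describes no analysis of hypoglycemic or hyperglycemic events and gives no glucose threshold for them.
- **Completion (Section 8).** All 80 subjects are expected to complete the procedures.

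**The concern.** A number of events has a clear meaning only when the observation time is known and common to all, or is divided out. Here the analysis set may hold any recording length from 7 to 14 days, so a count mixes how often a patient goes low or high with how long the sensor lasted. Total time in hypo- or hyperglycemia, and the share of patients with at least one event, depend on recording time in the same way.

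The error in expectation has one direction. Shorter recording lowers the expected count, so any sensor loss makes a primary and safety endpoint look better than it is.

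A common time unit also matters for interpretation. Section 2 expects a greater incidence of hypoglycemia in this population, but the study has no control group, so any such statement must lean on outside data. One of the studies described in Section 3 recorded for 48 hours. Against 14 days, the observation time alone differs by 14/2 = 7-fold.

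**Working it through.** The plan states no event rate, sample size derivation or other figure for the event endpoints, so there is nothing of its own to reproduce. The check is exposure arithmetic.

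**Inputs from the documents**
- Minimum recording for analysis: 7 days (Sections 12 and 16).
- Planned recording: 14 days (Sections 2 and 11).
- Subjects: 80, all expected to complete (Section 8).

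**Inputs assumed, because the documents give none**
- A constant event rate *r* per day, unrelated to how long the sensor lasts. Illustrative values are 0.1, 0.3, 0.5 and 1.0.
- The share *f* of analysed patients with only 7 days, the rest having 14.
- Poisson counts, where a probability or variance is needed.

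**Step 1. Two individuals with the same rate.** Expected count = *r* × days. The ratio is 14*r* / 7*r* = 14/7 = 2.0, whatever *r* is.

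| Assumed events/day | Expected count, 7 days | Expected count, 14 days |
|---|---|---|
| 0.1 | 0.7 | 1.4 |
| 0.3 | 2.1 | 4.2 |
| 0.5 | 3.5 | 7.0 |
| 1.0 | 7.0 | 14.0 |

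Total time below or above a threshold scales in the same way. The chance of at least one event is 1 − exp(−*r* × days). At 0.1 per day this is 1 − exp(−0.7) = 50% for 7 days and 1 − exp(−1.4) = 75% for 14 days.

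**Step 2. The cohort mean.** Mean days = 7*f* + 14(1 − *f*). Divided by 14, this is 1 − *f*/2.

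| Assumed share with 7 days | Patients out of 80 | Mean days | Mean count relative to full wear |
|---|---|---|---|
| 0% | 0 | 14.00 | 1.000 |
| 5% | 4 | 13.65 | 0.975 (2.5% low) |
| 10% | 8 | 13.30 | 0.950 (5% low) |
| 20% | 16 | 12.60 | 0.900 (10% low) |

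**Step 3. The same data with a denominator.** Dividing by recorded days turns the ratio in Step 1 into *r*/*r* = 1.0. In a simulation at 0.5 events per day with recording time uniform from 7 to 14 days, the mean raw count was 5.25 (0.5 × 10.5), against 7.0 at full wear. Total events over total days gave back 0.5 per day, or 7.0 per 14 days.

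**Step 4. What does not scale.** The length of a given event and its severity are properties of that event. Recording for longer adds events but does not make each one longer or worse.

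**The case against.** The strongest reply has four parts.

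1. **The plan is silent, not wrong.** Section 10 does not say that counts are raw or per patient, and incidence and time burden are compatible with a rate. This is correct, and nothing forbids a rate. But the stated measure is a number, and where Section 12 spells out an excursion-based summary (MAGE), it ends in a sum. Division by time cannot be taken as understood, and silence leaves the choice open until the data are seen. Whether counts are per patient or pooled makes no difference, since both grow with recording time.

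2. **The design is uniform.** Everyone is meant to wear the sensor for 14 days, and 7 days is a floor for analysis, not a planned exposure. This stands. A reader might infer that observation is unequal by design, or that the endpoint is two-fold wrong. The documents support neither. Two-fold is the extreme ratio of two expected counts, and the cohort effect rests on sensor loss that nobody has stated.

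3. **The harm is limited.** A reader might infer that subgroups with early sensor loss would look safer, or that the results could never be compared with another study. The subgroup work in Section 12 concerns regression slopes and intercepts only, so no comparison of event counts is planned. Recording time can be read from the CGM data, so a rate could still be derived later. Nor does short wear lower every observed count: a patient with no events in the lost days has the same count. Only the expectation falls.

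4. **The Day 14 visit is a separate matter.** Section 11 says: "Subjects will be advised to return to the research site on Day 14 to remove the CGM device for analysis". Counted visit to visit, Day 1 to Day 14 is 13 elapsed days, and the worst-case ratio becomes 13/7 = 1.86. It may equally be ordinary calendar-day numbering. Either way it applies to every patient and creates no inequality, so it gives no reason here to move the visit.

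**Conclusion.** The point holds as a missing denominator on a primary and safety endpoint and on one secondary endpoint. Under the plan's own 7-day rule and 14-day wear, expected counts and total time in hypo- or hyperglycemia can differ by up to 2.0-fold between two analysed patients with the same true rate.

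The downward shift in the cohort mean is 2.5% to 10% if an assumed 5% to 20% of patients have only 7 days and the others 14. It is negligible if all complete, as Section 8 expects. The figures assume a constant rate that is unrelated to sensor loss.

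The finding covers counts, total time and any-event proportions. It does not touch per-event duration or severity, or the HbA1c and fructosamine regressions. It is worth correcting before analysis because a clearly better measure is available from the same data, but it does not put the study in doubt.

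**What to change.** In Sections 10 and 12:

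- Define the number of hypoglycemic and of hyperglycemic events as events per patient-day of valid recorded sensor data. Equivalently, use a count model with the log of recorded time as offset.
- Define total duration as the percent of recorded time below and above thresholds stated in advance. The documents state none, and without them neither the events nor the percentages can be computed.
- State what counts as valid recorded time, in particular whether gaps count towards the 7 days.
- Report recorded hours per patient, and total events over total patient-days.
- Keep per-event duration and severity as they are.

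The cost is wording only, with no added data, visits or patients. The downside is that rates from short recordings are less precise: under a Poisson model the standard error of a 7-day rate is √(14/7) = 1.41 times that of a 14-day rate. An offset model, or total events over total days, gives those patients less weight. No change to the removal visit is needed for this point.

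### The subgroup comparison of regression lines uses intercepts extrapolated to HbA1c 0% and fructosamine 0; comparing fitted mean glucose at a prespecified in-range test value would be far more informative at almost no cost.

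*Combined protocol and SAP*

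**What the plan says.** Section 12 (Statistical Analysis) sets out the model: "A simple linear regression model will be applied to estimate the relationship between AMG and HbA1c". It states no centring or reference value for HbA1c, and the same analysis is to be repeated for fructosamine. The intercept is therefore fitted AMG at a test value of 0.

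From the overall model, "prediction of mean AMG together with 95% confidence intervals will be calculated at different levels of HbA1c". Patient factors come next: "Influence of factors such as age, gender on the relationship between HbA1c and AMG will be examined through a multivariate regression model". The form of that model, additive or with interaction terms, is not given. The subgroup sentence follows: "Slopes and intercepts of the regression equations for the individual subgroups will be compared to those of the simple linear regression model". It names two quantities, slope and intercept, and gives no test, alpha or decision rule.

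Section 10 (Endpoints) lists the intercept within a secondary end-point, alongside glucose at test levels: "Determination of HbA1c and serum fructosamine regression equation, slope, Y intercept, average glucose at different test levels".

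On size, section 8 says "There is an expected number of 80 recruited subjects from all aforementioned sites" and "We expect all patients will complete the research procedures", while section 12 adds "Patients with less than 7 days of CGM measurements will be excluded from analysis". The documents give no SD, effect size, subgroup size or alpha.

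**The concern.** The useful subgroup question is whether patients with the same HbA1c or fructosamine have different mean glucose depending on, say, age or sex. If a factor makes the marker read low or high, the line moves up or down within the observed range of the marker. The two quantities named for the subgroup comparison do not measure that movement well.

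- The intercept is the height of the line at a value no patient has. Its standard error is dominated by uncertainty in the slope.
- Because of that, the slope and intercept estimates nearly repeat each other, so the two comparisons supply little more than one.
- A difference in intercept need not mean a difference in glucose at any relevant test level, and similar intercepts need not mean agreement there.

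At stake is a misleading subgroup statement: apparent agreement where the same data could show a shift, or an impressive intercept gap where the lines coincide in the middle of the data.

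**Working it through.** The plan states no precision or power figure for this comparison, so there is none to reproduce.

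**Inputs.** From the documents: 80 subjects, all expected to complete. Assumed, because the documents are silent: HbA1c mean 7.5%, SD 1.0 to 2.0; fructosamine mean 300, SD 50 to 100; residual SD of AMG 20 to 40 mg/dL; a parallel shift of 20 mg/dL between subgroups; two subgroups of 40 (20 and 60 as a check); two-sided alpha 0.05.

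**Step 1: precision at zero against precision at the mean.** The SE ratio is about sqrt(1 + (mean/SD)²), and the slope-intercept correlation is about −mean/sqrt(mean² + SD²).

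| Marker | SD | SE ratio | Correlation |
|---|---|---|---|
| HbA1c, mean 7.5 | 1.0 | 7.6 | −0.991 |
| HbA1c, mean 7.5 | 1.5 | 5.1 | −0.981 |
| HbA1c, mean 7.5 | 2.0 | 3.9 | −0.966 |
| Fructosamine, mean 300 | 50 | 6.1 | −0.986 |
| Fructosamine, mean 300 | 100 | 3.2 | −0.949 |

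**Step 2: difference between two separately fitted lines.** With 40 per group and residual SD σ:

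- at the mean, SE = σ·sqrt(2/40);
- at zero, SE = σ·sqrt(2·(1/40 + 7.5²/(39·SD²))).

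For σ = 30 and HbA1c SD 1.5, the SE at the mean is 30·sqrt(0.05) = 6.7 mg/dL. At zero it is 30·sqrt(2·(0.025 + 56.25/87.75)) = 34.6 mg/dL. At roughly 2.80 SEs, the shift detectable with 80% power is about 19 mg/dL at the mean and about 97 mg/dL at zero.

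**Step 3: power for a 20 mg/dL parallel shift** (noncentral t, 76 df).

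| Residual SD | Intercept at 0: HbA1c SD 1.0 / 1.5 / 2.0 | At the mean HbA1c |
|---|---|---|
| 20 | 9% / 14% / 20% | 99% |
| 30 | 7% / 9% / 12% | 84% |
| 40 | 6% / 7% / 9% | 60% |

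A 3,000-run simulation at residual SD 30 gave 5%, 9% and 11% at zero and 83% to 84% at the mean. With subgroups of 20 and 60, power is 6% to 16% at zero and 48% to 97% at the mean. For fructosamine at residual SD 30 it is 8% to 15% at zero and 84% at the mean.

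**Step 4: subgroup against the overall line.** The plan compares each subgroup with the whole sample that contains it. For equal halves, that difference is half the between-half difference and its SE is also half, so power is unchanged.

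**Step 5: the opposite error.** Two lines that meet at HbA1c 7.5% and differ in slope by 5 mg/dL per 1% have intercepts 5 × 7.5 = 37.5 mg/dL apart, with no difference in fitted glucose at 7.5%.

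**The case against.** Four objections have force.

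1. *The plan already estimates glucose where the data lie.* This stands for the whole cohort: mean AMG at different test levels is both in the end-point and in section 12, and slope and intercept are the normal way to publish an equation. A reader might infer that the reported Y intercept is itself a defective end-point with almost no power. The documents do not support that, because no test of it is planned. Even a hypothetical test of the 80-patient intercept against a fixed reference would have 9% to 62% power for 20 mg/dL on the same assumptions: poor, but not uniformly negligible. Nothing, however, carries the level-specific estimates into the subgroup comparison.
2. *The multivariate model may settle the matter.* If it is additive, its subgroup coefficient is the vertical shift at every test value, with the same power as centring (60% to 99% for subgroups of 40). The form is not stated, and comparing subgroup slopes points to separate slopes.
3. *A joint test of slope and intercept does not depend on centring.* Correct. With a 2-df F test and 40 per group, power for the 20 mg/dL shift is 98%, 75% and 49% at residual SD 20, 30 and 40. The plan does not name such a test, and it would not say where or by how much the lines differ.
4. *The comparison may be only descriptive, and fitted values can be worked out from the subgroup equations.* A descriptive reading meets the same imprecision. Point estimates can be recovered from the equations, but their confidence intervals also need the covariance of the coefficients.

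**Conclusion.** The point holds for the subgroup comparison in section 12, conditional on separately fitted intercepts being compared on their own. In that case power for a 20 mg/dL shift is about 6% to 20%, against 60% to 99% for the same data at the mean HbA1c. Every input apart from the total of 80 is assumed. The absolute power figures depend on those assumptions, but the ordering does not change anywhere on the grid, because zero lies several SDs below the marker mean.

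A reader might go further and conclude that the study will report no difference between subgroups that do differ. That is not established: the plan leaves both the model form and the test open, and two reasonable choices would avoid the problem. The primary end-points and the whole-cohort equation are untouched. This is a nearly free improvement to a secondary, exploratory analysis.

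**What to change.** In section 12, replace the raw-intercept comparison with this:

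- Centre HbA1c and fructosamine at prespecified values inside the expected data range.
- For each factor and marker, fit one model with subgroup and subgroup-by-marker terms.
- Compare subgroups on fitted AMG at the prespecified value and on slope, each with a 95% CI.
- Keep the uncentred intercept only as part of the reported equation.
- If the quadratic model is used, its linear coefficient changes with centring, so compare fitted AMG at prespecified values rather than coefficients.

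The cost is a few sentences and a rescaled predictor, with no new data. For the linear model, fit, slope and predictions are unchanged. The chosen value need not equal the sample mean. Half an HbA1c point away, with SD 1.5 and residual SD 30, the SE is 30·sqrt(2·(0.025 + 0.25/87.75)) = 7.1 instead of 6.7 mg/dL, and power for 20 mg/dL is about 80% instead of 84%.
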